## 8.5 Statistical Analyses

Individual and mean ( $\pm$ SD) plasma concentration versus time curves will be presented for both linear and semi-log scales. Descriptive statistics (arithmetic and geometric means, standard deviation [SD], coefficient of variation [CV%], minimum [Min], maximum [Max], and median) of the plasma concentrations versus time will be presented as well for the PK parameters according to hepatic impairment groups included in the study (Mild, Moderate, Severe hepatic impairment, and Control). A graphical description of the relationship between hepatic impairment measures and PK will be presented.

For Part 1 plasma PK parameters, for each dose level separately using the SAS® GLM procedure, ANOVA will be performed on untransformed  $K_{el}$  and  $T_{1/2 el}$  and on ln-transformed  $AUC_{0-t}$ ,  $AUC_{0-inf}$ , and  $C_{max}$ , at the alpha level of 0.05 to compare groups (Control, Mild, Moderate, and Severe). Factors incorporated in the model will include Group as a fixed effect. For the analyses of each dose level, the data (dose-normalized for AUCs and  $C_{max}$ ) for the healthy control subjects group will be included for comparison purpose. The ratios with 90% CIs (Mild/Control, Moderate/Control, and Severe/Control) will be calculated for  $AUC_{0-t}$ ,  $AUC_{0-inf}$ , and  $C_{max}$ . Inter-subject Coefficient of variation will be estimated. For these analytes,  $T_{max}$  will be

analyzed non-parametrically (using the Hodges-Lehmann method) with point estimates and 90% CIs for the median differences of  $T_{\max}$  between groups (Mild-Control, Moderate-Control, and Severe-Control).

For Part 2 plasma PK parameters, for each day (as appropriate), using GLM procedures in SAS, ANOVA will be performed on untransformed  $K_{el}$  and  $T_{1/2\ el}$  and on ln-transformed  $AUC_{0-t}$ ,  $C_{\max}$ ,  $AUC_{0-12}$ ,  $AUC_{0-24}$ ,  $AUC_{0-inf}$ , and  $C_{trough}$  at the alpha level of 0.05 for nalbuphine and metabolites. Factors incorporated in the model will include Group as a fixed effect..

Sample code for the procedure in SAS® codes for ANOVA is specified below:

```
proc glm data=basepk;
  class GROUP;
  model VAR = GROUP / ss3 clparm alpha=0.1;
  means GROUP;
  lsmeans GROUP;
  estimate 'Mild vs. Control' GROUP 1 0 0 -1;
  estimate 'Moderate vs. Control' GROUP 0 1 0 -1;
  estimate 'Severe vs. Control' GROUP 0 0 1 -1;
run;
```

Derived calculations obtained from the ANOVA analyses will be performed as per the following:

- Inter Subject CV =  $100 * \text{SQRT}(e^{[MSE]} - 1)$ ;
- Ratio =  $100 * e^{\text{DIFFERENCE}}$ , where DIFFERENCE is the point estimate of hepatic impairment groups difference (e.g. Mild – Control, Mild – Control, and Severe - Control) on the ln-transformed scale; and
- 90% Confidence Limits =  $100 * e^{(\text{DIFFERENCE} \pm t_{(dfResidual)} * SE_{\text{DIFFERENCE}})}$ .

Sample code for the procedure in SAS® for nonparametric comparison (Mild vs Control):

```
proc npar1way hl alpha=.10 data= basepk;
  where GROUP in ('1','4');
  class GROUP;
  var Tmax;
  exact hl;
  ods select WilcoxonScores HodgesLehmann;
run;
```

Within each group, dose proportionality will be assessed by a visual assessment of the individual and mean nalbuphine PK parameters.

In the event that hepatic impairment has a clinically relevant effect on nalbuphine PK, the relationship between hepatic impairment and appropriate PK parameters for nalbuphine (e.g., CL/F, AUC0-12, AUC0-24, AUC0-t, AUC0-inf, AUC0-t, Ctrough, and Cmax) will be determined by a linear or non-linear regression.

Study results including the graphical description and the relationships between hepatic impairment and relevant pharmacokinetic parameters will be used to elaborate specific dosing recommendations if deemed clinically relevant.

Additional and exploratory statistical analysis may be performed.

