9.14 Dose Escalation Stopping Rules

Dose escalation can be stopped if any treatment-emergent adverse event (TEAE) occurs in a subject dosed with NAL ER during the study that, in the opinion of the Investigator, raises concerns about the safety and tolerability of a higher dose. In addition, the following dose escalation rules will apply.

Dose-limiting toxicity (DLT) in the hepatic-impaired subject population participating in this study is defined as the dose at which a confirmed Grade 3 adverse event develops in any 2 subjects, even if in two different organ systems, that is IP related and is unlikely to be related to the disease process. Overnight oximetry that drops more than 10% from a subject's baseline lowest value for a consistent period of 5 minutes will be considered a DLT TEAE.

Any subject who experiences a DLT TEAE will not receive further dose of study drug, and safety follow-up procedures will be performed.

9.14.1 Part 1 (SAD) Dose Escalation Procedures and Stopping Criteria for Subjects with Mild and Moderate Hepatic Impairment (Group 1 and Group 2)

Upon completion of the dosing of subjects with mild and moderate hepatic impairment (Group 1 and Group 2) in each of Cohorts 1 to 4 in Part 1 of the study, the safety data and nalbuphine PK parameters (if available or requested) will be reviewed by the Safety Committee to determine the continuation of the progression of Part 1 dose escalation and to evaluate the safety for that dose level to be included in Part 2 of the study (MAD).

If 2 subjects develop a DLT at the same dose, then that dose will be confirmed as DLT.

If 2 subjects develop a DLT at 2 different doses (eg, 108 mg and 162 mg), then the higher of the 2 doses (162 mg in this example) will not be pursued in remaining Group 1 and Group 2 subjects (if not already dosed).

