## **2. Study Objectives**

### **2.1 Primary Objectives**

- To evaluate the effect of hepatic impairment on nalbuphine extended release (NAL ER) pharmacokinetics (PK) as a function of dose.
- To evaluate the safety and tolerability of NAL ER in hepatic impaired subjects.

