### 3. Study Design

#### 3.1 General Design

This is a Phase 1, open-label PK and safety study of NAL ER in subjects with impaired hepatic function compared to healthy subjects. It will be performed in 2 parts:

- Part 1: single-ascending-dose (SAD) cohorts
- Part 2: multiple-ascending-dose (MAD) cohort

##### Part 1 (SAD) – Dose Cohorts 1 to 5

- Cohort 1 (27 mg): 6-8 subjects with mild hepatic impairment, 6-8 subjects with moderate hepatic impairment, and 4-6 subjects with severe hepatic impairment
- Cohort 2 (54 mg): 6-8 subjects with mild hepatic impairment and 6-8 subjects with moderate hepatic impairment
- Cohort 3 (108 mg): 6-8 subjects with mild hepatic impairment and 6-8 subjects with moderate hepatic impairment
- Cohort 4 (162 mg): 6-8 subjects with mild hepatic impairment and 6-8 subjects with moderate hepatic impairment
- Cohort 5 (highest dose tested in subjects with mild or moderate hepatic impairment): 6-8 healthy control subjects who have been appropriately age-, body mass index (BMI), and gender-matched to subjects with mild and moderate hepatic impairment from Cohorts 1 to 4

In Part 1 of the study (SAD), each of the cohorts will be dosed sequentially starting with the lowest dose for subjects with mild or moderate hepatic impairment. Subjects enrolled in Cohort 1 can also be enrolled in Cohorts 2, 3, and 4.

For each dose cohort, enrollment of subjects with mild (Group 1) or moderate (Group 2) hepatic impairment can be done in parallel. An evaluation of safety and tolerability of the combined mild and moderate hepatic impairment Group 1 and Group 2 subject data will be done at each dose level before proceeding to the next dose level.

Subjects with severe impairment (Group 3) will be enrolled with the 27 mg dose upon completion of SAD in subjects with mild and moderate impairment. After review of the safety and tolerability for the first 2 severe subjects dosed at 27 mg it will be determined whether or not to complete that dose level for the remaining severe subjects.

At the completion of all subjects dosed in the cohort, there will be an evaluation of safety and tolerability to determine whether to proceed to the next dose level for this group.

The drug pharmacokinetics in the hepatic impairment subject population will be compared relative to the healthy subject population (Cohort 5).

### Part 2 MAD – Dose Cohort 6

- Cohort 6: 6-8 subjects with mild and moderate hepatic impairment

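### Part 1 has no pre-specified estimate, with a confidence interval, of how the impairment effect changes with dose, and the per-dose ANOVAs leave the repeat dosing of subjects unused

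*SAP*

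**What the plan says.** SAP 2.1 gives the first primary objective as "To evaluate the effect of hepatic impairment on nalbuphine extended release (NAL ER) pharmacokinetics (PK) as a function of dose".

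SAP 8.5 sets the Part 1 analysis: "for each dose level separately using the SAS® GLM procedure, ANOVA will be performed on untransformed" elimination rate constant and half-life, and on log-transformed AUC0-t, AUC0-inf and Cmax. The model is stated in words ("Factors incorporated in the model will include Group as a fixed effect") and in code ("model VAR = GROUP / ss3 clparm alpha=0.1"). The single healthy cohort, dose-normalised, serves as control at every dose level. Protocol 12.3 specifies the same per-dose, group-only ANOVA.

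On repeat dosing, SAP 3.1 says "Subjects enrolled in Cohort 1 can also be enrolled in Cohorts 2, 3, and 4". Re-enrolment is optional. The notes to Protocol 4.1 also provide for naïve subjects entering Cohorts 2 to 4.

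Elsewhere in the plan, dose is handled as follows:
- SAP 8.5: visual assessment of dose proportionality within each group.
- SAP 8.8.1 (Part 1): dose-normalised descriptive statistics and plots of means against dose.
- SAP 8.8.2 (Part 2): an optional power model, written for a parallel design.
- Protocol 12.3: a power model within each group, if warranted.

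On variability, SAP 8.5 says "Inter-subject Coefficient of variation will be estimated" and computes it from the mean square error (MSE) of the same group-only ANOVA.

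**The concern.** The objective asks how the impairment effect varies with dose, but no planned Part 1 model contains dose. A reader would have to compare four sets of ratios that share the same control data and, in part, the same impaired subjects. The plan gives no interval for the difference between any two of them.

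Dose selection is a secondary objective. In addition, a Safety Committee judgement that PK is linear in dose in both Mild and Moderate may end the study before Part 2 (SAP 3.1, Protocol 9.14.5), and no numerical criterion is given. Part 1 could then be the only dose evidence, resting on plots and summaries.

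Two lesser matters follow from the same model:
- Subjects who leave before 162 mg drop out of the 162 mg ANOVA, and their lower-dose profiles are not used there. Protocol 9.14 says "Any subject who experiences a DLT TEAE will not receive further dose of study drug", and the replacement provision does not cover safety or tolerability withdrawals (SAP 3.5).
- The CV labelled inter-subject is computed from one observation per subject, so it contains within-subject variance as well.

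**Working it through.** **The plan's own figure.** Protocol 8.1 allows up to 78 subjects in Part 1. The cohort maxima give 4 × (8 + 8) + 6 severe + 8 healthy = 78, which reproduces it. That count treats every cohort as different people. If every impaired subject re-entered, there would be at most 8 + 8 + 6 + 8 = 30 individuals. Overlap is therefore possible but not guaranteed.

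**Inputs.**
- Total CV 50%: Protocol Table 1, AUC0-inf at 162 mg, 165/328 = 50.3%. Log-scale SD σ = √ln(1 + 0.5²) = 0.472.
- n = 8 per group, the planned maximum.
- Within-subject correlation ρ = 0.5 to 0.8: an assumption. Protocol 5.1.1.2 says only that intra-subject variability is the lower component, which points above 0.5.
- Share f of subjects present at both doses: an assumption.

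**1. Change in the Moderate/Mild log-ratio from 27 to 162 mg.** From raw cell means, SE = σ√[4(1 − fρ)/n].

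| Overlap | ρ = 0.5 | ρ = 0.8 |
|---|---|---|
| None, or treated as independent | 0.334 | 0.334 |
| Half (f = 0.5) | 0.289 | 0.259 |
| Full (f = 1) | 0.236 | 0.149 |

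For example, with full overlap and ρ = 0.8: 0.472 × √(4 × 0.2/8) = 0.149. As a 90% CI, the full-overlap values correspond to multiplying and dividing the estimate by exp(1.761 × 0.236) = 1.52 and exp(1.761 × 0.149) = 1.30 on 14 df. Treated as independent, the factor is exp(1.701 × 0.334) = 1.77 on 28 df.

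**2. Difference between the Mild and Moderate dose slopes, all four doses, full overlap.** SE = √[2σ²(1 − ρ)/(n·Sxx)], where Sxx = 1.866 for ln(27, 54, 108, 162). The 90% half-width is 0.289 if the doses are treated as independent, 0.205 at ρ = 0.5 and 0.130 at ρ = 0.8.

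**3. Selective loss, near-worst case.** Suppose the k of 8 subjects with the highest exposure at 108 mg all miss 162 mg. The two largest of 8 standard normal values have expectations 1.424 and 0.852. The expected shift in the 162 mg log-mean is −ρσ × (sum of the top k)/(8 − k).
- k = 1: exp(−0.5 × 0.472 × 1.424/7) = 0.953 at ρ = 0.5, and 0.926 at ρ = 0.8.
- k = 2: exp(−0.5 × 0.472 × 2.276/6) = 0.914 at ρ = 0.5, and 0.866 at ρ = 0.8.

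A simulation of 20,000 runs gives 0.953, 0.928, 0.916 and 0.867. In the same runs, a likelihood estimate that uses the three earlier doses returns 1.00, because loss there depends only on observed exposure.

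**4. CV label.** With one observation per subject, the expected MSE is the total variance (simulated 0.223; σ² = 0.223). A reported 50% corresponds to a between-subject CV of √(exp(ρσ²) − 1) = 34% at ρ = 0.5 and 44% at ρ = 0.8.

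**The case against.** **The plan does estimate impairment effects by dose.** This stands. Ratios with 90% CIs are given at every dose level. Each subject appears once per ANOVA, so no independence assumption is broken. A reader might infer that the intervals are invalid or that dose is ignored; the documents support neither. What is missing is a pre-specified estimate of the change across doses.

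**The precision gain depends on re-enrolment.** This also stands: re-enrolment is optional and naïve subjects may enter. The SAP's contrasts are each group against Control, so it plans no test of the Moderate/Mild change. A claim that the planned test is underpowered would be about a test that nobody proposed. The SEs above show what the data could support, not a failure of a planned interval.

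**Selective loss is hypothetical.** Largely right. No figure in the documents links exposure to withdrawal, and Protocol 5.1.1.1 describes earlier side effects as mostly mild to moderate. Two DLTs at one dose confirm that dose as a DLT under Protocol 9.14.1, so losing 2 of 8 and then running an ordinary 162 mg cohort fits tolerability withdrawals better than DLTs. Naïve entrants would dilute the effect. It is a risk, and the documents do not show that survivors will bias the top dose.

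**The CV point is labelling.** Agreed; no ratio or interval changes.

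**The per-dose ANOVA is specified in the protocol.** Agreed; Protocol 12.3 sets it, so the new model should be added beside it rather than replace it.

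**Conclusion.** The concern holds in a limited form. There is a gap between the first primary objective and the Part 1 analysis: no pre-specified estimate with an interval shows how the impairment effect changes with dose, although the design can supply one for Mild against Moderate. With CV 50%, 8 per group and full re-enrolment, a subject effect lowers the SE of the 27 to 162 mg change from 0.334 to between 0.236 and 0.149. The gain is smaller with partial overlap and zero without it.

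A low bias of the 162 mg ratio, about 5 to 7% with 1 of 8 lost and 8 to 13% with 2 of 8 lost, is a near-worst case that requires exposure-related loss. It sits inside a per-dose 90% CI factor of about 1.50 (n = 8, CV 50%).

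Control and Severe have one dose each, so no model can give a group-by-dose contrast for either. The calculations cover Part 1 only and do not support the same change in Part 2. This is a worthwhile, inexpensive improvement and does not invalidate the planned ratios.

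**What to change.** - Keep the per-dose ANOVAs, ratios and 90% CIs as Protocol 12.3 specifies.
- Add to SAP 8.5 and 8.8.1 a pre-specified mixed model for the Part 1 Mild and Moderate data on ln-AUC0-t, ln-AUC0-inf and ln-Cmax. Fixed effects: ln(dose) or dose level, group and their interaction. Random effect: subject. Use REML with Kenward-Roger degrees of freedom. Report each group's dose slope and the Mild-versus-Moderate difference with 90% CIs. The model accepts partial re-enrolment without change.
- State that no dose contrast is available for Control or Severe.
- Tabulate, by group and dose, how many subjects continued, entered new or left, with reasons.
- Label the MSE-based CV as total (between- plus within-subject), and report the two components from the mixed model.
- Record the addition in SAP section 4, which now states that nothing changed from the protocol. Protocol 12.3 already allows further analyses described in the SAP.

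The cost is SAP text and programming, with no new data. The downside is that the model assumes a common within-subject correlation across doses; the retained per-dose ANOVAs help to check the results against that assumption.

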Based on the overall safety and tolerability observed in the subjects with mild and moderate impairment, at the completion of all doses tested, it will be determined by the Safety Committee whether or not it is safe to proceed with dosing for the first 2 subjects with severe Impairment. After review of the safety and tolerability for the first 2 severe subjects dosed at 27 mg, it will be determined whether or not to complete that dose level for the remaining severe subjects.

At the completion of all subjects dosed in the cohort, there will be an evaluation of safety and tolerability to determine whether to proceed to the next dose level for this group.

The Safety Committee will be composed of at least the Investigators and one medically qualified Sponsor representative. Some adjustments to the currently outlined doses and/or dosing regimen may be implemented by the Safety Committee, but the dose to be administered in a given dose cohort will not exceed the one currently outlined in the protocol.

Drug administration in Part 2 of the study (MAD) may be initiated following satisfactory review of the safety and tolerability data from Groups 1 and 2 (mild and moderate impairment) from Part 1 of the study (SAD) by the Safety Committee. Depending on safety and tolerability as well as on available PK data, the dose escalation scheme may be modified such that intermediate dose levels are administered. The dosage regimen (once daily versus twice daily) will be confirmed following review of PK data from Part 1 of the study (SAD).

If in the judgement of the Safety Committee the Part 1 PK data demonstrates dose linearity across the dose range in both the mild and moderate hepatic impairment subjects (Group 1 and Group 2 subjects), such that PK modeling can be predictive of steady state dosing levels, a decision may be made to end the study without conducting Part 2 of the study

In Part 2 of the study (MAD), subjects will receive a single 27 mg dose in the morning of Day 1. Starting on Day 2, doses will be subsequently escalated for each subject to twice daily, 12 hours apart, 27 mg, 54 mg, 108 mg, and 162 mg over 13 days. On the last treatment day, (Day 13), subjects will receive a single 162 mg dose in the morning. Subjects will remain at each dose level for 2-3 days (minimum 5 consecutive doses) with dose escalation predicated on tolerability of the prior dose (See Section [9.14.4](#) for dose escalation stopping rules).

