## 8.7 Pharmacodynamic Analyses

For Part 2 only, the WI-NRS measure will be used to determine the severity of itch experienced by subjects with hepatic impairment at screening. Subjects will complete the two WI-NRS forms (the “Nighttime Itch” and the “Daytime Itch”) at the same time during the screening visit and the average will be taken to determine the baseline severity.

For all Cohort 6 subjects, WI-NRS measure will also be performed on a daily basis from Day -1 to Day 16, twice a day, once within an hour of completing their morning and evening meals (if applicable). Subjects will fill in the “Nighttime Itch” form in the morning and the “Daytime Itch” form in the evening.

PD parameters will be summarized at each protocol scheduled time point, by actual treatment. Actual values and actual changes from baseline will be presented.

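### The Part 2 by-day Group ANOVA uses exposures that are not dose-normalised, so if subjects leave the printed titration unevenly between groups, dose is mixed with hepatic function

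*SAP*

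**What the plan says.** **Analysis.** SAP 8.5 sets the Part 2 analysis by day ("For Part 2 plasma PK parameters, for each day (as appropriate), using GLM procedures in SAS") on ln-transformed AUCs, Cmax and Ctrough, and untransformed Kel and half-life, "at the alpha level of 0.05 for nalbuphine and metabolites. Factors incorporated in the model will include Group as a fixed effect". Protocol 12.3 plans the same by-day ANOVA. Neither normalises the Part 2 values for dose or includes a dose term. Part 1 is analysed by dose level, with dose-normalised AUCs and Cmax.

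**Dosing.** The titration table (Protocol 9.4, SAP Table 3-2) gives one morning dose on each profile day after Day 1: 27, 54, 108 and 162 mg on Days 4, 7, 10 and 13. Protocol 9.4 also says: "Subjects will remain at each dose level for 2-3 days (minimum 5 consecutive doses) with dose escalation predicated on tolerability of the prior dose". It adds that, depending on safety, tolerability and available PK data, "the dose escalation scheme may be modified such that intermediate dose levels are administered".

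**Stopping rules.** Protocol 9.14 states: "Any subject who experiences a DLT TEAE will not receive further dose of study drug". Once a DLT dose is confirmed, later subjects are dosed only through the maximum safe dose (MSD), on the table's own days. Protocol 9.11.1 then collects a 12-sample profile after the last dose, whatever that dose was.

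**Related handling.** SAP 8.8.2 gives dose-normalised Part 2 values for nalbuphine by group, as descriptive statistics. SAP 8.1 excludes subjects who missed doses or had significant deviations, but says so for descriptive statistics by time point, not for the ANOVA. For itch, SAP 8.7 says: "PD parameters will be summarized at each protocol scheduled time point, by actual treatment". SAP 8.5 has no such rule for PK.

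**The concern.** A by-day comparison is a by-dose comparison only while everyone is on the table. Once some subjects are a step lower, their AUC, Cmax and Ctrough fall roughly in proportion to dose, and a model with Group alone attributes that fall to hepatic function.

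The imbalance need not be random. If impairment raises exposure per mg and higher exposure causes intolerance, moderate subjects are the ones more likely to be on a lower dose. Their lower dose would then offset the increase that the analysis is meant to detect. With no hepatic effect, the same imbalance would look like one. The effect of impairment on PK as a function of dose is a primary objective, and SAP 8.5 uses the results for dosing recommendations.

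**Working it through.** The documents give no power or precision figure for the Part 2 ANOVA, so there is none to reproduce. As a check on the reading of Protocol Table 2, the accumulation ratio 50.88/31.53 = 1.61 matches the stated value.

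**1. Is the schedule itself balanced?** Yes. Counting doses in the table gives six at each of 27, 54, 108 and 162 mg, the sixth being the morning dose on the profile day. The text sets a minimum of five, so the table is not the only course it allows.

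**2. Size of the bias.** Suppose *k* of *n* moderate subjects are one step lower, all mild subjects are on schedule, and exposure is proportional to dose. On the ln scale,

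mean(Moderate) − mean(Mild) = ln(true ratio) − (k/n) × ln(step),

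so the implied ratio is multiplied by step^(−k/n). The step is 2 on Day 7 (54/27) and Day 10 (108/54), and 1.5 on Day 13 (162/108). The group size of 8 is the maximum in the protocol synopsis. The values of *k* are assumptions.

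| k of 8 | Days 7 and 10 | Day 13 |
|---|---|---|
| 0 | 1.00 | 1.00 |
| 2 | 2^(−2/8) = 0.84 | 1.5^(−2/8) = 0.90 |
| 4 | 2^(−4/8) = 0.71 | 1.5^(−4/8) = 0.82 |

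The reciprocals give the true increase that would be cancelled: 1.19- to 1.41-fold on Days 7 and 10, and 1.11- to 1.22-fold on Day 13.

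**3. Effect on the test.** This was simulated as a two-group test on the ln scale with 8 per group, two-sided alpha 0.05 and 40,000 runs per case. SD = sqrt(ln(1 + CV²)), with the AUCtau CVs of healthy subjects in Protocol Table 2: 39% at 108 mg twice daily (SD 0.38) and 33.7% at 162 mg twice daily (SD 0.33). The true ratios are assumptions.

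| Day | True ratio | Rejection rate, dose-normalised | k = 2, as planned | k = 4, as planned |
|---|---|---|---|---|
| 10 | 1.0 | 5% | 8% | 25% |
| 10 | 1.5 | 52% | 13% | 2% |
| 13 | 1.0 | 5% | 7% | 16% |
| 13 | 1.5 | 63% | 35% | 16% |

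**4. Does normalisation cost anything when all are on schedule?** No. ln(AUC/dose) = ln(AUC) − ln(dose), and ln(dose) is then the same constant for everyone, so the Group contrast and its test are unchanged. The reference dose also cancels.

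**5. Is proportionality a fair assumption over one step?** AUCtau ratios from Protocol Table 2 are 106.11/50.88 = 2.09, 240.37/106.11 = 2.27 and 351.15/240.37 = 1.46, against dose ratios of 2, 2 and 1.5. The largest departure is 2.27/2 = 1.13. With 4 of 8 one step lower, normalisation would leave a factor of 1.13^(−4/8) = 0.94 on Day 10, against 0.71 without it. These are healthy-subject data.

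**6. Last-dose profiles.** The sampling times after a last dose in Protocol 9.11.1 are identical to those of Day 13. A subject stopped at an MSD of 108 mg would therefore have a Day 13-type profile at two thirds of the Day 13 dose (108/162 = 0.67). The SAP does not say whether such profiles enter the Day 13 ANOVA.

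**The case against.** The strongest reply is that by day is by dose under the printed table. Part 1 normalises because each dose level is compared with controls who may have had a different dose. Cohort 6 has no control group, so a reader who infers that Parts 1 and 2 are inconsistent goes too far. That stands.

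A reader might also infer that the DLT rules leave subjects a step behind. They do not: a subject with a DLT stops, subjects on a confirmed DLT dose stop, and later subjects follow the table's days up to the MSD. These rules mainly produce missing days. If 162 mg were the DLT dose, later subjects would still be on 108 mg on Day 10, like everyone else. What remains is the unanswered question about last-dose profiles.

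Intermediate doses and the once- or twice-daily choice are tied largely to the review of Part 1. A change made before Part 2 starts applies to all. Only a change during enrolment, or escalation that differs between subjects, creates imbalance. The protocol describes no procedure for holding a subject at a level and then continuing, but its tolerability wording and 2-3 day range leave that open.

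No Moderate/Mild ratio is written for Part 2; the sample code has only contrasts against Control. The comparison is implied because Group is the sole factor and Cohort 6 contains only mild and moderate subjects.

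Finally, the normalised descriptive values in SAP 8.8.2 and the dosing listing in SAP 6.6 could expose an imbalance. They would not correct the ANOVA.

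**Conclusion.** The point holds in a conditional form. The SAP does not protect the Part 2 Group test against unequal doses on a profile day, although the protocol leaves room for them. The bias is zero if all subjects follow the table. With 2 to 4 of 8 moderate subjects one step lower, the implied ratio is multiplied by 0.84 to 0.71 on Days 7 and 10 and by 0.90 to 0.82 on Day 13. Those counts, their concentration in one group, and proportionality are assumptions.

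The documents do not support the stronger reading that the planned analysis is biased as written, or that a hepatic effect of a given size will be hidden: they give no basis for how many subjects would be off schedule. The stakes are also limited because Part 1 carries the comparison with controls and Part 2 may not be run. The change is still worthwhile, because it removes most of a possible bias and leaves the test unaltered when there is none.

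**What to change.** In SAP 8.5:

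- Keep the by-day Group ANOVA for Part 2, but run it on ln-transformed AUCs, Cmax and Ctrough, for nalbuphine and metabolites, normalised to the dose actually received at that profile. SAP 8.8.2 already plans such values descriptively for nalbuphine. Leave Kel and half-life as they are.
- List, by day and group, the subjects not on the scheduled dose, and repeat the ANOVA without them as a sensitivity analysis.
- State whether last-dose profiles from the DLT Follow-Up Period enter the Day 13 analysis.

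Keeping the analysis by day is preferable to regrouping by dose level reached. Regrouping would select subjects on tolerability and would leave open which profile counts when a subject has two at one level.

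The cost is SAP wording and a small amount of programming, with no change to dosing or sampling. The downside is reliance on approximate proportionality over one dose step, which Protocol Table 2 supports in healthy subjects only. The sensitivity analysis shows how far the result depends on the off-schedule profiles.
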